3.4 Handling of missing data

Imputation for missing data is not considered.

3.5 Handling of time course data

3.5.1 Calculation of Number of Days

Number of Days is calculated by the following formula:

- If after first study drug administration date, Number of Days (n) = date of interest – first study drug administration date + 1
- If prior to first study drug administration date, Number of Days (n) = date of interest – first study drug administration date

Number of Days are negative when the day of interest is prior to first study drug administration date, positive when day of interest is after first study drug administration date. Number of Days never takes 0.

3.5.2 Time Windows

For tables and figures, the visit will be defined as the following:

- For actual visits on EDC except unscheduled visit, end of treatment visit, early termination visit and end of study visit, the visit will be used as it is for analysis.
- For actual visits on EDC of unscheduled visits, the data from this visit will be used to calculate baseline, worst post baseline, and maximum post baseline only. Post baseline unscheduled visits will not be considered for by-visit analysis.
- For actual visits on EDC of end of treatment visit, early termination visit and end of study visit, the analysis visit will be as the following table. The day of administration of the investigational drug is defined as “Day 1”

Analysis visit	Reference date	Time window
Day 8	Day 8	Day 5 ~ Day 11
Day 15	Day 15	Day 12 ~ Day 18
Month 1	Day 29	Day 24 ~ Day 34
Month 2	Day 57	Day 52 ~ Day 62
Month 3	Day 85	Day 78 ~ Day 92
Month 4	Day 113	Day 106 ~ Day 120
Month 5	Day 141	Day 134 ~ Day 148
Month 6	Day 169	Day 162 ~ Day 176
Month 9	Day 253	Day 239 ~ Day 267
Month 12	Day 337	Day 323 ~ Day 351

For all listings, the visit will be displayed as the visit on EDC.

4. Statistical Analysis

4.1 Details of the Analysis Method

4.1.1 Summary Statistics

Continuous data except plasma PK parameters and pooled urine PK parameters will be summarized using descriptive statistics including number of patients, mean, standard deviation, SEM, median, minimum, and maximum.

Plasma PK concentration, urine PK concentration, Plasma PK parameters and pooled urine of PK parameters will be summarized using descriptive statistics including number of patients, number of BLQ and percentage (%), mean, standard deviation, SEM, CV(%), median, minimum, maximum, geometric mean, and geometric mean CV (%).

Categorical variables will be summarized using frequencies and percentages.

Results will be presented as the estimated value for each treatment group, Placebo, zilebesiran 300 mg, zilebesiran 600 mg, Total zilebesiran and Overall Total.

4.1.2 Baseline

For office BP, baseline is the mean seated office BP on Day 1 prior to receiving the first dose of study drug.

For 24-hour ABPM, baseline is the last measurement prior to receiving the first dose of study drug.

For HBPM, baseline is the average of all assessments during last week prior to receiving the first dose of study drug.

For all other endpoints, baseline is the last non-missing value (including unscheduled visit) prior to receiving the first dose of study drug.

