Abbreviations: ABPM=ambulatory blood pressure monitoring; ADA=anti-drug antibodies; AE=adverse event; AGT=angiotensinogen; BL=baseline; BMI=body mass index; D=day; ECG=electrocardiogram; EOT=End of treatment; EOS=End of study; ET=Early termination; FSH=follicle-stimulating hormone; HbA1c=hemoglobin A1c; HBPM=home blood pressure monitoring; ICF=Informed Consent Form; LFT=liver function test; M=month; PD=pharmacodynamics; PK=pharmacokinetics; RAS=renin-angiotensin system; SAE=serious adverse event.

Notes:

- When scheduled at the same time points and where feasible, the assessments of vital signs and blood sample collections for RAS biomarkers should be performed before 12-lead ECGs and physical examinations.
- In the Safety/PD Follow-up period, the frequency of HBPM assessments can be reduced after the first Safety/PD Follow-up visit per Investigator judgement.

Footnotes:

- ^a **All Day 1 assessments, except for postdose PK sample collection and ECG extraction (Table 2), are to be performed prior to dosing unless otherwise noted.**
- ^b When applicable, pregnancy test results must be known prior to dosing.
- ^c Clinical laboratory assessments and blood pressure measurements taken for eligibility must be performed after a minimum of 3 weeks of washout. Office blood pressure must be measured before the patient takes oral antihypertensive medications (if applicable).
- ^d An HBPM unit will be provided before the randomization visit to establish the HBPM baseline, and HBPM should be collected at least 3 times during the last week prior to Day 1. HBPM should be measured in the mornings at trough and at approximately the same time each day. HBPM measurements should be obtained upon waking, prior to breakfast/caffeine or taking morning oral medications. HBPM is not required on days when ABPM is being assessed.

Table 2: Pharmacokinetic and Electrocardiogram Time Points

Study Day	Sampling Time (hh:mm)	24-hour Holter ECG Extraction ^a	Blood PK Sample	Pooled Urine for PK ^b
Day-1	Predose (-24 h)	X		
Day 1	Predose (-1 h)	X	X	X
	Predose (-40, -30, -20, and -10 min)	X		
	00:30 (±5 min)	X	X	00:01-06:00
	01:00 (±5 min)	X	X	
	02:00 (±5 min)	X	X	
	03:00 (±5 min)	X	X	
	04:00 (±5 min)	X	X	
	06:00 (±10 min)	X	X	6:01-12:00
	08:00 (±15 min)	X	X	
	12:00 (±15 min)	X	X	12:01-24:00
	16:00 (±15 min)	X	X	
Day 2	24:00 (±2 hours)	X	X	
Day 3	48:00 (±6 hours)		X	

Abbreviations: ECG=electrocardiogram; hh:mm=hour:minute; PK=pharmacokinetics.

Notes:

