- The hour (±range) indicate sample collection timing relative to dosing. Precise PK sample times (hour and minute) are recorded. Refer to Section 6.4 for additional information on PK assessments.
- Patients should be supine for at least 10 minutes before each ECG is obtained. See Section 6.5.4 for additional information on ECG assessments.
- Sampling time windows do not apply to pooled urine PK unless otherwise stated.

^a On Day -1, 12-lead digital ECG data will be recorded using a 12-lead Holter monitor for a total of 1 hour (30 minutes before and after the 24-hour predose timepoint), and ECG data will be extracted within that window. Continuous 12-lead digital ECG data will be recorded on a 24-hour 12-lead Holter monitor starting on Day 1 (1 hour before dosing) through 24 hours postdose on Day 2. ECGs will be extracted from a 10-min window preceding the indicated time points.

^b Patients will be asked to void their bladders immediately before dosing (within 1 hour [±10 min] predose), and an aliquot will be taken from this sample as the 0 h sample. At the end of each collection interval, patients will be asked to void their bladders for a final time (eg, void bladder at 06:00 h for the 00:01 to 06:00 h sample), and all urine collected during the interval will be pooled.

TABLE OF CONTENTS

SPONSOR PROTOCOL APPROVAL2

INVESTIGATOR’S AGREEMENT3

PROTOCOL SYNOPSIS4

Study Design Schema7

Schedule of Assessments8

TABLE OF CONTENTS.....14

LIST OF TABLES18

LIST OF FIGURES18

LIST OF ABBREVIATIONS AND DEFINITIONS OF TERMS.....19

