7.1. Determination of Sample Size

The planned enrollment for this study is 36 patients, each treatment arm will include 12 patients. The sample size estimate is not based on the primary endpoint, which is a safety endpoint. Instead, sample size was estimated based on the secondary endpoint of percent change in AGT from baseline to Month 3 in Study 001. In Study 001, standard deviation (SD) for the percent change from baseline to Week 12 (Month 3) in the pooled zilebesiran arms was 42%. Assuming an SD of 0.42, the proposed sample size will provide more than 90% power to detect a 50% difference in percent AGT reduction at Month 3 between zilebesiran and placebo at a significance level of 0.05 (2-sided).

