2.8.2 PK 24-hour and Holter ECG Extraction

Analysis item	Analysis visit	Analysis timepoint
Blood PK Sample	Baseline	Predose
	Day 1	30 minutes postdose 1 hour postdose 2 hours postdose 3 hours postdose 4 hours postdose 6 hours postdose 8 hours postdose 12 hours postdose 16 hours postdose
	Day 2	24 hours postdose
	Day 3	48 hours postdose
Pooled urine for PK	Baseline	Predose
	Day 1	>0-6 hours postdose >6-12 hours postdose >12-24 hours postdose
24-hour Holter ECG Extraction	Baseline	Predose
	Day 1	30 minutes postdose 1 hour postdose 2 hours postdose 3 hours postdose 4 hours postdose 6 hours postdose 8 hours postdose 12 hours postdose 16 hours postdose
	Day 2	24 hours postdose

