12.3 ECG

12.3.1 Summary of Electrocardiogram Results by Visit

Target population	:	Safety Analysis Set
Analysis Items	:	ECG Ventricular rate, RR Interval, PR Interval, QRS Duration, QT Interval, QTcF Interval
Group	:	Placebo, Zilebesiran 300 mg, Zilebesiran 600 mg, Total zilebesiran, Overall Total
Time of analysis	:	Single 12-lead ECG: Refer to section 2.8.1 24-hour Holter ECG: Refer to section 2.8.2
Content of analysis	:	
 Calculate the summary statistics of measurement value, change from baseline and percent change from baseline for each quantitative item of the ECG test by groups and analysis time points. The baseline will be determined according to the Analysis Group The summary will be done for both Single 12-lead ECG and 24-hour Holter ECG.

12.3.2 Summary of Rhythm, Overall Interpretation of Electrocardiogram, Change from Baseline Electrocardiogram by Visit

Target population	:	Safety Analysis Set
Analysis Items	:	Rhythm, Overall Interpretation of ECG, Change from Baseline ECG
Group	:	Placebo, Zilebesiran 300 mg, Zilebesiran 600 mg, Total zilebesiran, Overall Total
Time of analysis	:	Single 12-lead ECG: Refer to section 2.8.1 24-hour Holter ECG: Refer to section 2.8.2
Content of analysis	:	
 Calculate the number of patients and the percentages by groups, analysis time points, ECG test and categories Category is as follows: Rhythm: Normal; Abnormal, not clinically significant; Abnormal, clinically significant; Not Evaluable; Missing Overall Interpretation of ECG: Normal; Abnormal, not clinically Significant; Abnormal, clinically significant; Missing Change from Baseline ECG: No significant worsening from baseline; Clinically significant worsening from baseline; Missing The summary will be done for both Single 12-lead ECG and 24-hour Holter ECG.
Definitions	:	
 The denominator of proportions is the target population by groups.

12.3.3 Shifts from Baseline to Worst Post-Baseline in QTcF Intervals on 24-hour Holter Electrocardiogram

Target population	:	Safety Analysis Set
Analysis Items	:	Worst Post-Baseline Value in QTcF Intervals, Maximum Change from Baseline in QTcF Intervals

Group	:	Placebo, Zilebesiran 300 mg, Zilebesiran 600 mg, Total zilebesiran, Overall Total

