Content of analysis	:	
 • Create shift table for baseline data and post-dose visit data by analysis items and categories • Category is as follows: Worst Post-Baseline Value (msec): <=450, >450 to 480, >480 to 500, >500, Missing, Total Maximum Change from Baseline (msec): <=30, >30 to 60, >60, Missing, Total
Definitions	:	
 • If the patient performs the test but there is not assessment result data will be analyzed as “Missing” • The denominator of proportions is the target population by groups.

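### The Holter QTcF baseline defaults to a single pre-dose extraction; averaging the Day 1 pre-dose extractions would cut noise at no cost

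*SAP*

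**What the plan says.** Protocol Table 2 schedules Holter extractions before dosing at -24 h on Day -1 and, on Day 1, at -1 h and in a row labelled "Predose (-40, -30, -20, and -10 min". Footnote a of that table starts the continuous Day 1 recording 1 hour before dosing and adds: "ECGs will be extracted from a 10-min window preceding the indicated time points".

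SAP 4.1.2 sets out how baseline is formed for office BP, 24-hour ABPM and HBPM, and covers everything else with one sentence: "For all other endpoints, baseline is the last non-missing value (including unscheduled visit) prior to receiving the first dose of study drug". SAP 2.8.2 lists one pre-dose baseline entry for the Holter data and no averaging rule. The only baseline wording specific to ECG is in SAP 12.3.1: "The baseline will be determined according to the Analysis Group". The SAP does not define that term.

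The baseline feeds the by-visit changes in SAP 12.3.1 and the shift table in SAP 12.3.3, whose categories are "Maximum Change from Baseline (msec): <=30, >30 to 60, >60, Missing, Total".

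**The concern.** The protocol collects a cluster of pre-dose ECGs ten minutes apart, and the SAP gives all but the last of them no role in the change from baseline. Elsewhere in the same section the plan does average: the HBPM baseline is the average of the last week's readings, and the office BP baseline is the mean seated value.

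A single reading matters most in SAP 12.3.3. There each patient is classified by the maximum of ten post-dose changes, all taken against the same baseline. One chance low baseline reading raises all ten differences together and can create a >30 msec flag; a chance high one lowers all ten. ECG is among the assessments supporting the primary safety objective, and each arm has 12 patients, so one flagged patient is 1/12, or 8%, of an arm.

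**Working it through.** The documents state no QTcF variance or expected outlier rate, so there is no figure of the plan's own to reproduce.

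**Inputs from the documents**
- Baseline rule: last non-missing pre-dose value (SAP 4.1.2). With complete data this is the -10 min extraction.
- Day 1 pre-dose extractions: -1 h, -40, -30, -20 and -10 min (Protocol Table 2). The window for -1 h runs from -70 to -60 min, but recording starts at -60 min (footnote a). That extraction may therefore not exist. The other four are secure, so the number averaged is k = 4.
- Post-dose extractions: nine on Day 1, from "30 minutes postdose 1 hour postdose 2 hours postdose 3 hours postdose 4 hours postdose 6 hours postdose 8 hours postdose" through 12 and 16 hours, and one on Day 2 at "24 hours postdose", giving 10 (SAP 2.8.2).
- Sample size: "The planned enrollment for this study is 36 patients, each treatment arm will include 12 patients" (Protocol 7.1).

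**Assumptions**
- s is the within-patient SD of one extraction. It is not in the documents; values from 5 to 12 msec are shown.
- r is the share of pre-dose variance common to all pre-dose readings.
- Errors are normal, post-dose errors are mutually independent, and there is no drug effect.

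**Variance of one change from baseline**
- Single baseline: s² + s² = 2s².
- Mean of four, r = 0: s²(1 + 1/4) = 1.25s². Reduction 1 − 1.25/2 = 37.5%.
- Mean of four, r = 0.5: s²(1 + 0.5 + 0.5/4) = 1.625s². Reduction 1 − 1.625/2 = 18.75%.
- Mean of four, r = 0.75: s²(1 + 0.75 + 0.25/4) = 1.8125s². Reduction about 9%.
- If the -1 h extraction does exist, five readings with r = 0 give 1.2s², a reduction of 40%. The choice between four and five hardly matters.

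**Chance that a patient's maximum change exceeds 30 msec by noise alone**

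Let v be the baseline error variance divided by s²: 1 for a single reading, r + (1 − r)/4 for the mean of four. Then

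P = 1 − ∫ φ(z) Φ((30 + z·s·√v)/s)¹⁰ dz,

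evaluated numerically. The expected number of flagged patients is 36P:

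| s (msec) | Single | Mean of 4, r = 0 | Mean of 4, r = 0.5 | Mean of 4, r = 0.75 |
|---|---|---|---|---|
| 5 | 0.00 | 0.00 | 0.00 | 0.00 |
| 6 | 0.07 | 0.00 | 0.02 | 0.03 |
| 8 | 1.07 | 0.14 | 0.52 | 0.78 |
| 10 | 3.76 | 1.22 | 2.55 | 3.18 |
| 12 | 7.28 | 3.89 | 5.89 | 6.65 |

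These counts are for all 36 patients. Per arm, divide by 3: with a single baseline, 0.36 at s = 8 and 1.25 at s = 10.

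With 60 in place of 30, the single baseline gives at most 0.01% per patient up to s = 10, and 0.2% at s = 12. False >60 msec flags are therefore negligible up to s = 10.

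**The case against.** The case for leaving the plan alone has several parts.

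- **The -10 min baseline is inferred.** No sentence names it; it follows from a catch-all, and SAP 12.3.1 has ECG-specific wording. This stands as a caution. However, that wording rests on an undefined term and supplies no averaging rule. Read strictly, the plan uses one reading; read generously, the Holter baseline is undefined. Both need the same clarification.
- **The size is uncertain.** This stands. The effect is negligible at s = 5 to 6 msec. The footnote does not say how many ECGs each window yields or whether they are averaged; if each time point is already a replicate mean, s is smaller. Adjacent ten-minute windows are probably correlated, so the independent-error column is an upper bound on the gain. Averaging within the hour before dosing also does not remove diurnal drift.
- **The consequence is limited.** This also stands. Protocol 7.2 makes the analyses primarily descriptive with no formal testing, there is a concurrent placebo arm, the primary endpoint in Protocol 7.2.8 is the frequency of patients with treatment-emergent AEs, and individual Holter data are listed (SAP listing 13.32).

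A reader might infer that the rule tilts the QTcF comparison toward or away from zilebesiran. The documents do not support that: the same rule applies to every arm, so it adds noise and not direction. A reader might also set the expected counts beside the 12 patients per arm and conclude that one or two false flags per arm are likely. The counts are per 36; one per arm is reached only near s = 10, and there the average still leaves 1.2 to 3.2 per 36 across the correlations shown. Finally, Table 2 read alone suggests that four other Day 1 extractions go unused; only three are secure besides the -10 min one.

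**Conclusion.** The point holds as a free precision improvement. As written, the SAP makes the Holter QTcF baseline one extraction and leaves at least three other Day 1 pre-dose extractions out of the change from baseline. Averaging the four secure readings lowers the variance of change by up to 37.5%, and by 18.75% if half the pre-dose variance is shared. In none of the settings examined did averaging raise the false-flag rate.

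The practical benefit rests on a within-patient SD that the documents do not give. It is almost nothing at 5 to 6 msec, about half to one fewer false >30 msec patient among 36 at 8 msec, and about one to two and a half fewer at 10 msec, for shared variance between one half and zero. It is smaller still with stronger correlation. The noise is equal across arms and the table is descriptive, so this warrants a SAP clarification and does not call the trial's safety conclusions into question.

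**What to change.** In SAP 4.1.2, add a Holter-specific rule: baseline is the mean of all non-missing Day 1 pre-dose extractions. The non-missing wording covers the doubtful -1 h extraction. Apply this baseline in SAP 12.3.1 and 12.3.3, state how the Day -1 extraction is used, and define or delete the term Analysis Group in 12.3.1.

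The cost is a few sentences in the SAP. No new data, visits or procedures are needed. Making the change before unblinding avoids a choice of baseline made after the results are known.

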4.1.3 Percentage of patients

The percentage is calculated by the following formula (unless otherwise indicated):

$$\text{Percentage(\%)} = \frac{\text{Applicable patients}}{\text{Patients per group in the analysis population}} \times 100$$

Unless otherwise noted, the denominator will be based on the analysis population.

4.1.4 Change from baseline and Percent change from baseline

The change from baseline and the percent change from baseline will be calculated using the following formula.

Change from baseline = Postdose value - Baseline value

$$\text{Percent of change(\%)} = \frac{\text{Postdose value} - \text{Baseline value}}{\text{Baseline value}} \times 100$$

4.1.5 CV(%)

$$\text{CV(\%)} = \frac{\text{SD}}{\text{Mean}} \times 100$$

$$\text{Geometric CV(\%)} = [\text{sqrt}(\exp(s^2) - 1) \times 100] \quad s^2: \text{Variance on the natural logarithm scale}$$

4.2 Display Digit of the Calculated Value

4.2.1 Display digits of summary statistics, etc.

Mean, SD, SEM, Median

Round to 1 more decimal place than the display digit.

Min, Max

Round to the same number of decimal places as the display digit.

4.2.2 Representation orders of magnitude of proportions (%), CV(%), and geometric CV(%)

Round to the first decimal place.

5. Patient Disposition

5.1 Summary of Screening Failure

Target population	:	All Screened Patients
Group	:	Overall Total
Content of analysis	:	Calculate the number of patients and the percentages by groups for the following items: Screening Pass Screen failure Reason for Screen failure 
 • Inclusion/Exclusion Criteria • Serious Adverse Event • Death, specify • Lost to follow-up • Physician Decision • Study Terminated by Sponsor • Withdrawal by Patient • Other, specify
Definitions	:	All Screened Patients are all cases in which informed consent was obtained. The denominator of proportions is the target population by groups.

5.2 Patient Disposition for 6-Month DB Period and Safety/PD Follow-up Period

Target population	:	Randomized Patients
-------------------	---	---------------------

Group	:	Placebo, Zilebesiran 300 mg, Zilebesiran 600 mg, Total zilebesiran, Overall Total
Content of analysis	:	Dosed Completed 6-Month DB period Withdrawal from study during 6-Month DB period Completed Study Withdrawal from study During the Safety/PD Follow-up Period Primary reason for withdrawal from study during 6-Month DB period 
 • Adverse Event • Death • Lost to Follow-Up • Physician Decision • Pregnancy • Protocol Deviation • Study Terminated by Sponsor Primary reason for withdrawal from study during Safety/PD Follow-up period 
 • Adverse Event • Death • Lost to Follow-Up • Physician Decision • Pregnancy • Protocol Deviation • Study Terminated by Sponsor
Definition	:	The denominator of proportions is the target population by groups.

5.3 Summary of Data Sets Analyzed

Target population	:	Randomized Patients
Group	:	Placebo, Zilebesiran 300 mg, Zilebesiran 600 mg, Total zilebesiran, Overall Total
Content of analysis	:	Calculate the number of patients and the percentages by groups for the following items: 
 • Safety Analysis Set • Pharmacokinetic Analysis Set • Pharmacodynamic Analysis Set • Full Analysis Set
Definitions	:	The denominator of proportions is the target population by groups.

5.4 Summary of Protocol Deviations

Target population	:	Randomized Patients
Group	:	Placebo, Zilebesiran 300 mg, Zilebesiran 600 mg, Total zilebesiran, Overall Total
Content of analysis	:	Calculate the number of patients and the percentages by groups for the following items: 
 • Patients with at least one protocol deviation • Patients with at least one major protocol deviation • Reason for protocol deviation
Definitions	:	All Screened Patients are all cases in which informed consent was obtained.

		
The denominator of proportions is the target population by groups. Multiple answers are counted in each reason. Before randomization: Deviation date <= randomized date. 6-Month DB period: 6-Month DB period start date <= Deviation date <= 6-Month DB period end date. Safety/PD Follow-up period: Safety/PD Follow-up period start date <= Deviation date <= Safety/PD Follow-up period end date.

--	--	---

6. Demographic and other baseline characteristics

6.1 Demographic and Other Baseline Characteristics

Target population	:	Safety Analysis Set
Group	:	Placebo, Zilebesiran 300 mg, Zilebesiran 600 mg, Total zilebesiran, Overall Total
Content of analysis	:	
 Summaries of demographic and other baseline characteristics will be presented for all patients in the target population. For categorical data and ordinal data, calculate the number of patients and percentages by groups. For continuous data, calculate the summary statistics by groups.
Definitions	:	
 The denominator of proportions is the target population by groups.

[Background items]

Data	Items [Units]	Classification	Remarks
Continuous	Age at Informed Consent [years]	-	
	Height [cm]	-	
	Weight (Baseline) [kg]	-	
	BMI [kg/m ²]	-	
	eGFR [mL/min/1.73m ²]	-	
Categorical	Age category [years]	<65, >=65	
	Sex	Male, Female	
	Race	Asian	
	BMI Category [kg/m ²]	<25, >=25 to <30, >=30	
	eGFR category [mL/min/1.73m ²]	>=90, >=60 to <90	
	Baseline ABPM category [mmHg] Systolic blood pressure	<145, >=145	

